7.1.2. Major Secondary PK Endpoints

Major secondary endpoints include PK exposure at Week 52 (the trough concentrations at Week 52) and the Bayesian AUCss at Week 52 (from population PK modeling and simulation).

7.1.2.1. Definition

C_{trough,wk52}: Serum golimumab concentration at Week 52.

7.1.2.2. Analyses Methods

The analysis of the major secondary PK endpoint will be performed via population PK modeling using NONMEM as described in Section 7.1.1.2.

7.1.3. General PK Summaries

PK samples for measuring serum golimumab concentrations will be collected from all subjects at the specified visits as shown in the schedule of events of the protocol. Samples will be collected at Weeks 0, 4, 8, 12, 20, 28, 52, 100, 148, 196 and 244. Two samples, one pre-infusion and another post-infusion, will be collected at Weeks 0, 4, and 12. An additional random PK sample for serum golimumab concentration will be collected from all subjects at any time between Weeks 0 and 8 other than at the time of the Week 0, 4 and 8 visits; this sample must be collected at least 24 hours before or after a study agent infusion.

All PK evaluations will be based on the subjects who receive at least 1 infusion of golimumab (PKE analysis set).

No imputation for missing concentration data will be performed. Pre and post infusion serum concentrations will be summarized separately.

The data analysis of serum golimumab concentrations includes the following:

- Summary of serum golimumab concentrations at each visit
- Summary of serum golimumab concentrations at each visit by body weight quartiles.
- Summary of serum golimumab concentrations at each visit by BMI quartiles.

- Summary of serum golimumab concentrations at each visit by BSA quartiles.
- Summary of serum golimumab concentrations at each visit by age (2 to <6 years, 6 to <12 years, 12 to <18 years).
- Summary of serum golimumab concentrations at each visit by CRP quartiles and CRP categories (<0.1 mg/dL, ≥0.1 mg/dL; <1.0 mg/dL, ≥1.0 mg/dL).
- Proportion of subjects without detectable serum golimumab concentration at each visit.
- Summary of serum golimumab concentrations at each visit by antibodies to golimumab status.
- Median serum golimumab concentrations plotted over time.

In addition, the relationship between serum golimumab concentrations and antibody to golimumab status, safety and efficacy may be explored using graphical displays. Median serum golimumab concentrations will be plotted. Box plots of serum golimumab concentrations will be plotted by percentage subjects who achieved JIA ACR 30 responses.

For summary statistics of serum golimumab concentrations, concentration values below the lower limit of quantification will be treated as zero. Once a subject meets one of the following dosing deviation criteria, the subject's data will be excluded from the by-visit data analyses from that point onwards.

Dosing deviation criteria:

- Discontinue IV study agent administrations.
- Skipped an IV administration.
- Received an incomplete / incorrect IV dose.
- Received an additional IV dose.

In addition, if a subject has an administration more than 7 days earlier or later than the scheduled dosing date, the concentration data collected between such a dosing visit and the subsequent dosing visit will be excluded from the by-visit data analyses. For visits prior to Week 28, if the PK sampling time deviates more than 3 days earlier or later than the scheduled date, the PK concentration at this visit will be excluded from the by-visit data analyses. Additional exclusions for incongruous PK data to be implemented based on Janssen SOP-07948v2.

Population PK analyses will be performed to characterize the population PK parameters based on the available golimumab concentration data obtained through the Week 28 visit. The population pharmacokinetic approach will also be used to identify and quantify any significant covariates such as demographic characteristics (including but not limited to body weight, sex, and age).

PK analyses will be summarized through the following time periods:

- Through Week 28
- Through Week 52
- Through Week 244

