 - TB and/or a positive QuantiFERON®-TB Gold test result (or a positive tuberculin skin test result in countries in which the QuantiFERON®-TB Gold test is not approved/registered or the tuberculin skin test is mandated by local Health Authorities), unless active TB can be ruled out and appropriate treatment for latent TB can be initiated prior to the next administration of study agent and continued to completion. Indeterminate QuantiFERON®-TB Gold test results should be handled as in Section 9.1.2. Subjects with persistently indeterminate QuantiFERON®-TB Gold test results may continue without treatment for latent TB if active TB is ruled out, their chest radiograph shows no abnormality suggestive of TB (active or old, inactive TB) and the subject has no additional risk factors for TB as determined by the investigator. This determination must be promptly reported to the Sponsor's medical monitor and recorded in the subject's source documents and initialed by the investigator.
 - A subject receiving treatment for latent TB discontinues this treatment prematurely or is noncompliant with the therapy.

All subjects who discontinue study agent infusions during the study will be followed for approximately 8 weeks after the last infusion is administered.

Note: The visit that is approximately 8 weeks after the last study agent infusions is referred to as the "final safety follow-up visit," which may occur at a scheduled or an unscheduled visit.

Subjects who discontinue study agent infusions but do not terminate study participation will have the following assessments performed at the final safety follow-up visit:

- Safety evaluation including AE review, TB evaluation, and the collection of a blood sample for routine laboratory analyses, determination of the presence of ANA/anti-double-stranded deoxyribonucleic acid (dsDNA) antibodies, and antibodies to golimumab; after Week 52, other safety evaluations are performed at the discretion of the investigator (vital signs, review of systems, uveitis evaluation).
- Concomitant medication review (after Week 52, medications should be reviewed and documented in subject's source records; medications used to treat or associated with AEs and SAEs should be recorded in the source document as well as the CRF).
- Efficacy evaluations (joint assessments, JIA assessments, and collection of blood sample for CRP) through Week 52 only.

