- Blood samples drawn for measurement of golimumab concentration for all subjects at the final safety follow-up visit.

If a subject discontinues study treatment before the end of the study, assessments should be obtained approximately 8 weeks after the last infusion of study agent.

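### SAP 7.1.3's exclusion after stopping golimumab removes a valid Week 28 or Week 52 trough when the last correct infusion was at Week 20 or Week 44

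*SAP*

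**What the plan says.** SAP 7.1.3 states that once a child meets a dosing deviation criterion, "the subject's data will be excluded from the by-visit data analyses from that point onwards". One criterion is "Discontinue IV study agent administrations". The others are "Skipped an IV administration", "Received an incomplete / incorrect IV dose" and an additional dose.

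The SAP's sampling list is by study week: "Samples will be collected at Weeks 0, 4, 8, 12, 20, 28, 52, 100, 148, 196 and 244". It does not name the final safety follow-up visit, and none of the summaries listed in that section is for it. SAP 7.3, by contrast, promises a listing of antibody status for discontinuers who complete safety follow-up.

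Protocol 10.2 sets that visit about 8 weeks after the last infusion and says it is one "which may occur at a scheduled or an unscheduled visit". For children who stop infusions but stay in the study it requires "Blood samples drawn for measurement of golimumab concentration for all subjects at the final safety follow-up visit". Protocol Table 1 carries the sample in its follow-up column. Footnotes m and n of that table put the single Week 28 and Week 52 samples before any infusion at those visits.

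The Week 28 trough is half of the primary endpoint (SAP 7.1.1), the Bayesian AUCss being the other half. The Week 52 trough is part of the major secondary endpoint (SAP 7.1.2).

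**The concern.** Take two children dosed identically and on schedule at Weeks 0, 4, 12 and 20. One is stopped before Week 28 and the other goes on. Both give a sample at Week 28, before any further dose, and the two samples measure the same thing. The rule keeps one and drops the other because of a dose that had not yet been due when the interval was sampled. The observed trough summary is thereby conditioned on a later event. The same holds for Week 44 and Week 52.

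This matters if children who stop tend to have low levels. One route is plausible from the protocol's own background: in the sponsor's subcutaneous paediatric study, antibody titres above 1:100 went with lower steady-state troughs (Protocol 1.1.2.2). The observed concentrations also form part of the paediatric-adult comparison (SAP 7.1.1.2), and the share of children without detectable drug is a planned summary in its own right.

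**Working it through.** **The plan's own precision figure.** Half-width of the 95% CI for the mean = 1.96 × CV / √100. At CV 30%, 40%, 50%, 60% and 70% this gives 5.88%, 7.84%, 9.80%, 11.76% and 13.72%. All five agree with SAP Table 1 after rounding, so ±9.8% (CV 50%) is a fair yardstick.

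**Which follow-up samples fall on a PK visit.** Infusion weeks are from Protocol Table 1; the follow-up sample is at last infusion + 8 weeks.

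| Last infusion (week) | Follow-up sample (about week) | Scheduled PK visit? | All doses due before that visit given? |
|---|---|---|---|
| 0 | 8 | yes | no (Week 4 missing) |
| 4 | 12 | yes | yes |
| 12 | 20 | yes | yes |
| **20** | **28** | **yes** | **yes** |
| 28 | 36 | no | yes |
| 36 | 44 | no | yes |
| **44** | **52** | **yes** | **yes** |

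Only a last dose at Week 20 or Week 44 puts the follow-up sample on Week 28 or Week 52. For every other stopping time in the table, the rule removes nothing from those two trough summaries.

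**Size at Week 28 or Week 52.** Let 100 children be kept with mean trough 1, and let d excluded children have mean trough r. The documents give neither d nor r; both are assumed. Overstatement of the mean = (100 + d)/(100 + d·r) − 1.

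| d | r = 0.75 | r = 0.5 | r = 0 (undetectable, scored zero) |
|---|---|---|---|
| 3 | 0.7% | 103/101.5 − 1 = 1.5% | 103/100 − 1 = 3.0% |
| 5 | 1.2% | 105/102.5 − 1 = 2.4% | 105/100 − 1 = 5.0% |

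At r = 1 there is no shift.

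**Tails and strata.**
- Suppose 5 of the 100 kept children are undetectable, and so are the 3 or 5 excluded. The proportion becomes 8/103 = 7.8% or 10/105 = 9.5%, against a reported 5%.
- Ages 2 to under 6 are expected to be about 10% of 120, or 12 children (Protocol 3.1). Leaving out one undetectable child overstates that stratum's mean by 12/11 − 1 = 9.1%.

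**Early stoppers and steady state.** A rough one-compartment check uses the adult medians in Protocol 1.1.2.1: 41.56 µg/mL after the Week 4 infusion and 0.28 µg/mL at Week 12, 56 days later. k = ln(41.56/0.28)/56, which gives an apparent half-life of about 7.8 days. The 8-week level after one dose, relative to steady state, is 1 − exp(−56k) = 0.993, or 0.938 if the half-life is 14 days. Such samples are close to steady-state troughs but not identical to them.

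**The case against.** Several points on the other side stand.

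- **Scope.** A reader might infer that all concentrations after stopping are thrown away. The documents do not say so: the exclusion is confined to by-visit analyses. SAP 7.1.3 bases population PK on the available data through Week 28 and states no dosing-deviation exclusion for it. That model supplies AUCss and is the stated analysis route for the Week 52 endpoint (SAP 7.1.2.2). Whether the separate population PK plan applies the rule cannot be seen.
- **Cause.** A reader might also infer that the rule is why the Week 28 and Week 52 troughs describe children still on drug. Mostly it is not: children who stop at other times have no sample at those visits.
- **Size.** Counting the whole planned loss of 20 in 120 as recoverable gives 120/110 − 1 = 9.1% (half trough) or 120/100 − 1 = 20% (undetectable). That is a ceiling, not a scenario. The 20 include children who give no PK sample, and the rest would stop at various weeks. Nor can the 19 of 173 who stopped through Week 16 of the subcutaneous study be carried over. On this schedule such a child was last dosed by Week 12 and sampled by about Week 20.
- **Direction.** Low exposure in those who stop is not established. The subcutaneous study found similar efficacy across trough quartiles and no apparent PK difference by flare (Protocol 1.1.2.2), although 14 of its 19 early stoppers left for lack of efficacy.
- **Timing.** The SAP does not date the point from which exclusion runs. If stopping is decided at the Week 28 visit after the pre-dose draw, the sample arguably precedes the deviation. The clear case is a child stopped between Week 20 and Week 28.
- **Design choice.** Restricting troughs to children dosed as scheduled is coherent in a study with no hypothesis test.

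The last argument does not rescue the rule for the case at issue, because that child was dosed as scheduled for the whole sampled interval.

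**Conclusion.** The point holds in a narrow form. The stopping criterion removes a correctly timed, correctly dosed trough from the observed Week 28 summary (last dose Week 20) and from the Week 52 summary (last dose Week 44). The remaining follow-up samples are given no place in SAP 7.1.3.

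The shift in the overall mean is probably small. The illustrated 1.5% to 5% all lies inside the SAP's ±9.8%, and rests on assumed counts of 3 to 5 per 100 kept and assumed troughs of half or zero. The proportion undetectable and the youngest age group are more exposed, again on assumed counts. No effect on AUCss or the population PK model has been shown. This is a worthwhile, inexpensive correction to a stated rule, not a threat to the study's conclusions.

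**What to change.** In SAP 7.1.3, reword the stopping criterion so that, after discontinuation, only samples taken later than 8 weeks (plus the visit tolerance) after the last correct, on-schedule infusion are excluded. Samples after a Week 20 or Week 44 last dose then stay in the Week 28 and Week 52 trough summaries. Dating the rule from the last infusion also removes the ambiguity about when exclusion starts. Name the tolerance explicitly, because SAP 2.1 and SAP 7.1.3 use different limits for off-schedule infusions (3 days through Week 28, and 7 days).

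Add one row for the final safety follow-up sample: n, median, IQR and percentage undetectable, by antibody status. Keep it separate, since children who stopped after one or two doses are not exactly at steady state. A Week 8 sample from a child last dosed at Week 0 belongs only there, because it lacks the Week 4 dose that the other Week 8 samples reflect. It would also help to state whether the exclusion applies to the population PK data set.

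The cost is SAP wording and one table row. The protocol already collects the samples.

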7.2. Pharmacokinetic/Pharmacodynamic Analyses

The relationship between serum golimumab concentrations and efficacy measures may be explored, and the results will be reported in a separate technical report.

7.3. Immunogenicity

Blood samples will be collected to examine the formation of antibodies to golimumab at the specified visits as shown in the schedule of events of the protocol. For subjects who discontinue IV study agent administrations, samples will be collected at their safety follow-up visit.

The data analysis of antibodies to golimumab includes the following:

- The antibody status (positive, negative) of subjects will be summarized. For subjects who discontinue IV study agent administrations and complete safety follow-up, a listing of their antibody status will be presented.
- The relationship between antibody to golimumab status and efficacy and safety will be assessed at major assessment time points (Weeks 28, 52 and 252). JIA ACR 30 responses by antibody to golimumab status; infusion reactions by antibody to golimumab status.
- The relationship between antibody to golimumab status at Week 28 and antibody to golimumab status at Week 52 will be explored.
- The onset of antibody to golimumab formation will be summarized
- The duration of antibody to golimumab will be summarized.
- The serum golimumab concentrations by antibody to golimumab status will be presented graphically.

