With regards to immunogenicity, 40.1% of subjects developed antibodies to golimumab using the recently developed drug tolerant immunoassay analyses. The new drug tolerant immunoassay is more sensitive compared with assays used previously in adult golimumab RA studies and allows the detection of antibodies to golimumab despite detectable serum golimumab levels. Among subjects who were randomized and remained on golimumab 30 mg/m² SC + MTX, 30.8% developed antibodies to golimumab; antibody titers tended to be low. When evaluating the effects of immunogenicity on PK, efficacy, and safety, it was found that positive anti-golimumab antibody status decreased steady-state trough golimumab concentrations when the titer levels were >1:100. However, the effect of antibodies on efficacy was less sensitive, requiring higher titers >1:1000 in order to correlate with apparent reductions in efficacy. Since only approximately 5% of subjects with JIA developed anti-golimumab antibodies with titers >1:1000, it was determined that immunogenicity was not a contributing factor to lack of achievement of the primary endpoint in CNTO148JIA3001. Additionally, positive anti-golimumab antibody status did not appear to be associated with a higher incidence of injection-site reactions.

The proportion of subjects who reported an AE through Week 48 was 87.9%. The most commonly reported SOC of AEs was Infections and infestations (67.1%), and were predominantly URTIs and nasopharyngitis. There was no marked difference in AEs reported between Week 16 and Week 48 for subjects randomized to placebo (82.9%) and those randomized to continued golimumab treatment (78.2%); however, it needs to be noted that all subjects in randomized withdrawal portion of the study were exposed to golimumab for

16 weeks before re-randomization. Serious adverse events were reported by 13.3% of subjects. The most commonly reported SAE was worsening of JIA (6.4%). Serious infections were reported in 2.9% of subjects (pneumonia, urinary tract infection, herpes zoster, URTI, and pyelonephritis), and there were no deaths, malignancies, or demyelination events through Week 48. There were no reports of active TB and no serious opportunistic infections. Through Week 48, the number of subjects with abnormal alanine aminotransferase (ALT) measurements (and no concomitant treatment for latent TB, which may affect liver function tests [LFTs]) was 29.5% (51/167), 39 of the 51 subjects had elevations <3×ULN.

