9.3.4. Immunogenicity Assessments (Antibodies to Golimumab)

Antibodies to golimumab will be evaluated in serum samples collected from all subjects according to the Time and Events Schedule (ie, Weeks 0, 4, 8, 12, 28, 52, 100, 148, 196, and 244). Additionally, serum samples should also be collected at the final visit from subjects who are discontinued from treatment or withdrawn from the study. These samples will be tested by the Sponsor or Sponsor's designee.

Serum samples will be screened for antibodies binding to golimumab and the titer of confirmed positive samples will be reported. Other analyses may be performed to verify the stability of antibodies to golimumab and/or further characterize the immunogenicity of golimumab.

The incidence of antibodies to golimumab during the study will be determined.

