11.5. Immunogenicity Analyses

The occurrence and titers of antibodies to golimumab during the study will be summarized over time for all subjects who receive an administration of golimumab and have appropriate samples collected for detection of antibodies to golimumab (ie, subjects with at least 1 sample obtained after their first golimumab administration).

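### SAP 7.3 leaves out the antibody titer summary that protocol 11.5 requires, and relates antibodies to concentration and JIA ACR 30 by positive/negative status only

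*SAP*

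**What the plan says.** Protocol 11.5 (Immunogenicity Analyses) states: "The occurrence and titers of antibodies to golimumab during the study will be summarized over time". The synopsis says the same. Protocol 9.3.4 provides the data, since "the titer of confirmed positive samples will be reported".

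The SAP works from status alone. Section 7.3 opens its list with "The antibody status (positive, negative) of subjects will be summarized". For efficacy and safety it plans "JIA ACR 30 responses by antibody to golimumab status; infusion reactions by antibody to golimumab status". It adds the relation of Week 28 to Week 52 status, the onset and duration of antibodies, and a graph of concentrations by status. Section 7.1.3 lists "Summary of serum golimumab concentrations at each visit by antibodies to golimumab status". No titer summary, category or cut-off appears anywhere in the SAP.

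Protocol 1.1.2.2 describes the sponsor's subcutaneous (SC) study in children. There, "positive anti-golimumab antibody status decreased steady-state trough golimumab concentrations when the titer levels were >1:100". The effect on efficacy was less sensitive, "requiring higher titers >1:1000 in order to correlate with apparent reductions in efficacy". The same section gives 40.1% of all subjects as antibody-positive, 30.8% among those randomised to and remaining on golimumab (titers mostly low), and about 5% of subjects above 1:1000.

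**The concern.** The first part is a plain mismatch. The protocol promises a summary by titer and sends the analysis details to the SAP, which does not contain it. The protocol's amendment log lists no change to Section 11.5, so nothing suggests that the requirement came after the SAP.

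The second part is what the two-way split can show. In the SC study it was titer, not status, that went with lower troughs and lower efficacy. The sponsor used the small share above 1:1000 to argue that immunogenicity did not explain that study's missed primary endpoint. The present SAP provides no table from which that argument could be repeated or refuted. Pooling all positives mixes a few high-titer children with many low-titer ones, and a real loss of response in the few can look like a negligible difference. Immunogenicity is a stated secondary objective, and the Week 28 trough is part of the primary endpoint.

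**Working it through.** **The plan's own figures.** Neither document gives a size or precision for any antibody comparison, so there is nothing on this point to reproduce. The only precision table, SAP Table 1, concerns the mean concentration. It is recovered at all five CVs by 1.96 × CV/√100 (for example 1.96 × 50%/10 = 9.8%).

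**Inputs.** From protocol 1.1.2.2: 40.1% positive (all SC subjects), 30.8% positive (continued golimumab), about 5% of subjects above 1:1000. From protocol 1.1.2.2, for illustration only: JIA ACR 30 of 87.3% at Week 16. From SAP 1.2: about 120 enrolled, about 100 at Week 52.

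**Share of positives above 1:1000.** f = P(titer above 1:1000)/P(positive).
- All subjects: 5/40.1 = 12.5%.
- Continued golimumab: 5/30.8 = 16.2%, taking the 5% to hold in that group too.

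In 100 to 120 children this means 40 to 48 positives (at 40.1%) or 31 to 37 (at 30.8%), of whom 5 to 6 exceed 1:1000.

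**Dilution for efficacy.** If positives at or below 1:1000 respond like negatives and those above lose D points, the expected positive-versus-negative difference is f × D.

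| Assumed loss D above 1:1000 | f = 12.5% | f = 16.2% |
|---|---|---|
| 20 points | 2.5 | 3.2 |
| 40 points | 5.0 | 6.5 |
| 60 points | 7.5 | 9.7 |

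**Could the diluted difference be seen?** Take D = 40 and 87.3% in negatives. The rate in positives is then 82.3% (f = 12.5%) or 80.8% (f = 16.2%). The 95% half-width is 1.96 × √[p₊(1−p₊)/n₊ + p₋(1−p₋)/n₋]:
- 40.1% positive: 14.5 points at N = 100, 13.2 at N = 120.
- 30.8% positive: 16.0 points at N = 100, 14.6 at N = 120.

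A difference of 5.0 to 6.5 points is well inside that noise.

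**What a split at 1:1000 gives.** It shows the full 40 points (47.3% against 87.3%), but on 5 of 100 or 6 of 120 children. The half-width is 44.3 or 40.4 points, and the normal approximation is rough at such counts. Individual listings are therefore more useful than an interval.

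**Troughs.** The share of positives above 1:100 is not given. It cannot be below the share above 1:1000, so it may be much larger. As pure illustration, if it were 25%, 50% or 75%, a 50% fall in mean trough in those children would appear as 12.5%, 25% or 37.5% across all positives. The direction is known; the amount is not.

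**The case against.** The strongest reply is that the size of the dilution is borrowed from another regimen. The cut-offs come from SC golimumab 30 mg/m² every 4 weeks; this trial gives 80 mg/m² intravenously every 8 weeks. Median troughs were 0.95 to 1.16 µg/mL in the SC study but 0.22 to 0.28 µg/mL in adults on the IV regimen. With less drug at trough, lower titers might matter too, and the dilution would then be smaller. The SC titers come from a drug-tolerant immunoassay, while protocol 9.3.2 says only that the assay is validated, so the scales may differ. All of this stands. It limits the magnitude but does not supply the missing titer summary.

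A second reply is that the SAP covers part of the ground: concentrations by status, the proportion without detectable drug at each visit, and antibody onset and duration. The separate population PK plan might also use titer as a covariate. None of the listed items uses titer, and a PK covariate would give neither the titer summary nor a display of response by titer.

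A third is that a row of 5 or 6 children settles nothing. That is true of inference, but the SAP plans no hypothesis tests, so small numbers are a reason for cautious labelling and listings, not for omission.

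Some stronger readings are tempting and not supported:
- A reader might infer that the SAP decided against titers. It is silent; its list is introduced as inclusive and withdraws nothing.
- A reader might infer that the infusion-reaction table is diluted as well. No titer threshold for reactions is documented. The SC study reports only no apparent association between status and injection-site reactions.
- A reader might infer that the analysis will probably show no antibody effect on exposure. No number in the documents supports that.

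**Conclusion.** The mismatch between protocol 11.5 and SAP 7.3 is certain and rests on no assumption. The consequence for efficacy is plausible and of moderate confidence: a positive-versus-negative contrast would keep about one eighth to one sixth of any effect confined to titers above 1:1000. This range assumes that the SC incidence, the roughly 5% high-titer share and the 1:1000 threshold apply to IV dosing and to this assay, and that lower titers have no effect on response. It is a range: a single eight-fold figure would use only the all-subjects rate, whereas the continued-golimumab rate is closer to this single-arm trial and gives about six-fold. For troughs only the direction can be stated. Nor do the documents say that antibodies are a main cause of low troughs here. Because the trial is descriptive, the harm is a table that looks reassuring when it cannot be informative, not lost power for a test. The change should be made, but it does not threaten the primary analysis.

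**What to change.** 1. In SAP 7.3, add the summary of antibody titers over time that protocol 11.5 and the synopsis require.
2. In SAP 7.3 and 7.1.3, add descriptive displays in four categories: negative, ≤1:100, >1:100 to 1:1000, and >1:1000. Show trough concentration by the titer at that visit, so that a past peak does not class a later trough. Show JIA ACR 30 by the titer at that visit, with highest titer to date as a supporting view.
3. Label these displays exploratory and state that the cut-offs come from the SC study.
4. List titer, trough and JIA ACR 30 over time for each high-titer child.
5. Keep the positive/negative split as a supporting presentation, and leave infusion reactions by status as planned.

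The cost is SAP wording, some table columns and one listing. Titers are already to be reported, and protocol 9.3.2 provides a golimumab concentration for every antibody sample, so no visit, sample or assay is added. The downside is the sparse top category, about 5 or 6 children, which can be described but not compared.
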